3.2.2. Secondary Endpoints

- The pharmacokinetic assessment of C_{max} , T_{max} and $AUC_{(0-t)}$ as measured by the validated Battelle Mouse Neutralization Assay (MNA) for serotypes A and B
 - Pharmacokinetic samples will be tested by MNA at pre-dose and on Days 4, 30, 60, 90, and 120 for Cohorts 1-3.
 - Pharmacokinetic samples will be tested by MNA at pre-dose, 2-hours post-dose (future use), and on Days 4, 30, 45, 60, 90, and 120 for Cohort 4.
- The assessment of C_{max} , T_{max} , half-life (α and β), MRT, and $AUC_{(0-t)}$ for each of the monoclonal antibodies of G03-52-01 as measured by a validated electrochemiluminescence assay (ECLA) or validated enzyme-linked immunosorbent assay (ELISA).
 - Pharmacokinetic samples will be tested by ECLA or ELISA at pre-dose, 2, 4, 8, 24, 48, and 72 hours post injection, and on Days 4, 8, 15, 30, 45, 60, 90, and 120 for Cohorts 1-3.
 - Pharmacokinetic samples will be tested by ECLA or ELISA at pre-dose, 6 hours post-dose, and on Days 1, 2, 4, 8, 15, 30, 45, 60, 90, 120, and 180 for Cohort 4.
- Samples will be tested to evaluate presence of anti-drug antibodies (ADA) collected for all cohorts.
 - Samples will be tested for ADA at pre-dose, 15, 30, 45, 60, 90, and 120 for Cohorts 1-3.
 - Samples will be tested for ADA at pre-dose and on Days 45, 60, 90, 120, and 180 for Cohort 4.

4. STUDY DESIGN

This is a Phase 1, single-center, placebo-controlled, double-blind, dose-escalation study to evaluate the safety and tolerability of G03-52-01 in healthy adults. This is a first-in-human study consisting of four Cohorts of ten subjects each. Each subject will receive a single IM injection of G03-52-01 or placebo.

Table 1: Cohorts

Cohort	Dose of G03-52-01	Number of Subjects
1	10 mg	10 subjects (8 active, 2 placebo)
2	25 mg	10 subjects (8 active, 2 placebo)
3	50 mg	10 subjects (8 active, 2 placebo)
4	100 mg	10 subjects (8 active, 2 placebo)

Schedule for Subjects

Subjects in Cohorts 1-3 will participate in the study for approximately 150 days, including a 28-day screening period, up to 12-hour inpatient stay and approximately 120-day follow-up after study product administration. Subjects will remain at the clinic and not be eligible for discharge until 8 hours after the IM injection. Last follow up visit scheduled at Day 120.

Subjects in Cohort 4 will participate in the study for approximately 210 days, including a 28-day screening period, up to a 12-hour clinic stay and approximately 180-day follow-up after study product administration. Subjects will remain at the clinic and not be eligible for discharge until approximately 8 hours after the IM injection. Last follow up visit scheduled at Day 180.

The end of the study is defined as the date of the last visit of the last subject in the study.

Schedule for Cohorts

Since this is a first-in-human study, administration of the study products to subjects in a cohort will occur over a period of up to two weeks to allow careful observation of individuals for adverse events. Two sentinel subjects within each cohort will be admitted initially and will be administered a single IM injection, and the randomization scheme will be designed to ensure that one subject will receive G03-52-01 and the other will receive placebo. The dosing of the remaining eight subjects within that cohort will not be initiated until at least 24 hours have passed and no adverse events have occurred that meet halting criteria, and no safety signals have occurred that in the opinion of the investigator warrant further investigation. The remaining eight subjects in the cohort will be admitted as scheduled without delay. An alternate subject will be admitted to the unit for each two-subject group. Up to four alternates per cohort will be recruited. Dose escalation will not occur until safety data through Day 8 is reviewed by the Safety Review Committee (SRC) composed of the Principal Investigator (PI), Ology Bioservices Medical Monitor, and the ICON Medical Monitor.

4.1 Study Enrollment and Withdrawal

Only subjects who meet all of the inclusion and none of the exclusion criteria will be eligible for enrollment into this study. No exemptions are granted on Inclusion/Exclusion Criteria in DOD-sponsored studies.

Forty healthy male and female subjects, ages 18 to 45 years old, will be enrolled in four cohorts. Up to four alternates per cohort will be recruited. Alternates who meet all eligibility criteria may effectively have their check-in at the same time as the lead two subjects and be rolled over into the next group within that cohort but will not be dosed until 24 hours after the initial two subjects are dosed (Cohorts 1-3). Alternates not enrolled into a dosing group within a cohort are eligible for enrollment into the next group for that cohort. Alternates not enrolled into the cohort are eligible for enrollment in subsequent cohorts but would have to undergo re-screening with the exception of the viral serology labs listed in section 7.5.1.1 if more than 28 days have passed since collection of screening laboratory parameters.

4.1.1 Subject Inclusion Criteria

All must be answered yes for the subject to be eligible for study participation

1. Informed consent understood and signed
2. Healthy male or healthy, non-pregnant, non-lactating female
3. Willingness to comply and be available for all protocol procedures
4. Between 18 and 45 years of age on the day of IM injection
5. Body Mass Index (BMI) of ≥ 18.5 and $\leq 35 \text{ kg/m}^2$
6. If the subject is female and of childbearing potential, she has a negative serum pregnancy test at screening and negative urine test within 24 hours prior to IM injection
 - *Note: A woman is considered of childbearing potential unless post-menopausal (≥ 1 year without menses) or surgically sterilized via bilateral oophorectomy, or hysterectomy or bilateral tubal ligation or successful Essure placement with documented confirmation test at least 3 months after the procedure.*
7. If the subject is female and of childbearing potential, she agrees to practice abstinence from sexual intercourse with men or use acceptable contraception during participation in the study
 - *Note: Acceptable contraception methods are restricted to effective devices (Intrauterine Contraceptive Devices)*
8. The hemoglobin, platelet count, white blood cell count and absolute neutrophil count are not below the LLN and $\leq \text{ULN} \times 10\%$
 - *Abnormalities in mean corpuscular volume (MCV), mean corpuscular hemoglobin (MCH), mean corpuscular hemoglobin concentration (MCHC), red cell distribution width (RDW), mean platelet volume (MPV), and nucleated red blood cell count (NRBC CT), which are included in a complete blood count with differential, will not be exclusions.*
9. The urine dipstick results on protein, glucose and blood are negative or trace
 - *Note: Menstruating females failing inclusion criteria due to a positive blood on urine dipstick may be retested following cessation of menses.*

- *Note: When a urine dipstick is more than trace positive for blood (whether a menstruating female or other subjects), that subject would not be excluded if the urine microscopic exam shows <5 rbcs/hpf.*

10. Chemistry screening laboratory tests as outlined in Section 7.5.1.4 are in the normal reference range

- *Note: The following exceptions to laboratory normal reference ranges are allowed: Creatinine, Blood Urea Nitrogen (BUN), total bilirubin, AST, ALT, lipase, amylase, Prothrombin Time (PT), Partial Thromboplastin Time (PTT) below the lower limit of normal (LLN); CK less than 400U/L; Glucose, potassium, total protein, and alkaline phosphatase with a toxicity grade of 1 is allowable; albumin above the upper limit of normal (ULN).*
- *Laboratory values that are outside the range of eligibility but are thought to be due to an acute condition or due to laboratory error may be repeated once.*

11. The urine drug screen is negative

12. Breathalyzer test is negative

13. Available for follow-up for the duration of the study

14. Agrees not to participate in vigorous activity 72 hours prior to dosing through day 15 post dosing

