6.5.2. Safety Laboratory Tests

The following laboratory tests will be done at screening and end of study. Subjects should be fasting. This means no food or drink (other than water) for at least eight hours prior to sampling.

Safety labs with a Grade 1 value (Appendix B) will not exclude a subject from participation but will serve as their baseline value.

- Hematology: hemoglobin, WBC with differential, absolute neutrophil count and platelet count. MCV, MCH, MCHC, RDW, MPV, which are included in a complete blood count with differential, will not be graded.

- Chemistry: serum creatinine, BUN, calcium, total bilirubin, direct bilirubin, indirect bilirubin, alkaline phosphatase, PT, PTT, INR, ALT, AST, sodium, potassium, and total CK.
- Urinalysis: dipstick: Urine protein, blood and glucose must be negative or trace. Menstruating females failing with a positive blood on urine dipstick may be retested following cessation of menses.

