10. STATISTICAL CONSIDERATIONS

10.1. Sample Size Considerations

This is a Phase 1 study first in humans with four dosing Cohorts and no formal sample size calculations based on testing a statistical hypothesis were constructed. Four dosing groups of ten each with eight participants assigned the active group and two assigned to the control group are

practical and provide sufficient information for a total sample size of 40 for a Phase 1 trial primarily designed to assess safety. If ten subjects are studied, then the probability of at least one subject experiencing an event of toxicity can range from 0.728 to 0.996 assuming true event rates between 0.15 and 0.5. Additionally, if no events are observed in a cohort of six dosed subjects receiving G03-52-01 the upper bound of an exact 95% confidence interval for the true proportion is 0.46.

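### Inclusion criterion 8 prints an upper blood-count limit (ULN × 10%) below its own lower limit, and its lower limit conflicts with the Grade 1 rule in protocol 6.5.2 and SAP 3.16

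*Protocol*

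**What the plan says.** Protocol 4.1.1, criterion 8, sets two bounds on four tests. Hemoglobin, platelets, "white blood cell count and absolute neutrophil count are not below the LLN and" must then satisfy an upper bound printed as ≤ ULN × 10%. The note beneath it exempts only red-cell indices, mean platelet volume and nucleated red cells.

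The inclusion list is conjunctive: "All must be answered yes for the subject to be eligible for study participation". Protocol 4.1 adds: "No exemptions are granted on Inclusion/Exclusion Criteria in DOD-sponsored studies".

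Protocol 6.5.2 lists hematology, chemistry and urinalysis tests done at screening and end of study, and says: "Safety labs with a Grade 1 value (Appendix B) will not exclude a subject from participation". SAP 3.16 repeats this rule. The SAP does not restate criterion 8.

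Appendix B gives the site's normal ranges and the toxicity grades. No other section restates or explains the upper limit in criterion 8.

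**The concern.** An eligibility limit has to define a range that some value can satisfy. Taken literally, 10% of the ULN is a very low number, and it is paired with a requirement not to fall below the LLN. If the two bounds cross, the criterion cannot be applied as printed and someone has to decide what it means. The protocol allows no exemptions, so that decision needs to be written down.

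A second question arises at the lower bound. Criterion 8 excludes values below the LLN; 6.5.2 and SAP 3.16 admit Grade 1 values. If the Grade 1 low bands lie below the LLN, the two rules give opposite answers for the same subject.

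What is at stake is who enters the study and what is reported as an eligibility deviation. Protocol 14.6 treats any noncompliance as a deviation, SAP 7.10 lists and summarizes deviations, and SAP Listing 16.2.4.3 reports eligibility by subject.

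**Working it through.** The plan has no calculated figure to reproduce here. Criterion 8 is a stated limit, and protocol 10.1 says that "no formal sample size calculations based on testing a statistical hypothesis were constructed".

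**Step 1: is the interval in criterion 8 empty?** The inputs are the normal ranges in Appendix B. The interval from LLN to 0.10 × ULN contains a value only if 0.10 × ULN ≥ LLN, that is, if ULN/LLN ≥ 10.

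| Test | LLN | ULN | 0.10 × ULN | ULN/LLN | Interval |
|---|---|---|---|---|---|
| Hemoglobin, male (g/dL) | 12.3 | 17.3 | 1.73 | 1.41 | empty |
| Hemoglobin, female (g/dL) | 10.9 | 14.6 | 1.46 | 1.34 | empty |
| Platelets (10³/mm³) | 150 | 400 | 40 | 2.67 | empty |
| WBC (cells/mm³) | 4,000 | 10,000 | 1,000 | 2.50 | empty |
| Neutrophils (cells/mm³) | 1,700 | 7,000 | 700 | 4.12 | empty |

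Each value of 0.10 × ULN also falls in Appendix B's own Grade 3 range: hemoglobin below 10.0 (male) or 8.5 (female), platelets below 100, WBC below 1,500, neutrophils below 1,000.

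The race-specific rows of Appendix B do not change this. They imply limits of 2,500 to 9,000 for WBC in African American males (0.10 × ULN = 900), and 2,500 to 11,000 in females (1,100). For neutrophils they imply an LLN of 1,300; with the printed ULN of 7,000, 0.10 × ULN is 700. All three intervals are empty.

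**Step 2: does the Grade 1 rule agree with the lower bound?** The inputs are the general Grade 1 rows of Appendix B.

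| Test | Grade 1 low band | LLN | 6.5.2 and SAP 3.16 | Criterion 8 |
|---|---|---|---|---|
| Hemoglobin, male | 11.2–12.2 | 12.3 | not excluded | excluded |
| Hemoglobin, female | 9.8–10.8 | 10.9 | not excluded | excluded |
| Platelets | 120–149 | 150 | not excluded | excluded |
| WBC | 2,500–3,999 | 4,000 | not excluded | excluded |
| Neutrophils | 1,300–1,699 | 1,700 | not excluded | excluded |

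The whole Grade 1 band lies below the LLN in every row. This conflict does not depend on how the upper-limit expression is read.

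**Step 3: does the Grade 1 rule supply an upper limit?** Only for WBC. Its general Grade 1 high band is 10,001–15,000, with a top of 14,000 for African American males and 15,000 for African American females. For hemoglobin, platelets and neutrophils, Appendix B grades low values only, so criterion 8 is the only source of an upper limit and gives none that can be used.

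**Step 4: how far apart could readings be?** The documents do not state the intended limit. Purely as an assumption about intent, a tolerance of 10% above the ULN would give 1.10 × 10,000 = 11,000 for WBC. A WBC from 11,001 to 15,000 would then fail that reading of criterion 8 and pass the general Grade 1 rule.

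**The case against.** The strongest objection is that the upper-limit defect rests on one operator in a formula read from PDF. If a plus sign was misread as a multiplication sign, that part may disappear. This cannot be settled from the text supplied, which is why the fix begins with the source document. It does not touch the Grade 1 conflict in Step 2.

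It can also be said that 6.5.2 concerns safety laboratory tests. Screening tests have their own section, and Table 2 shows safety labs from baseline onward. There is something in this, but 6.5.2 and SAP 3.16 both place the tests at screening, and a sentence about exclusion from participation is an eligibility rule.

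The exceptions under criterion 10 do not help: they concern the chemistry screen. The allowance to repeat a value once changes no limit.

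Inconsistent application is less likely than in a multicenter trial. There is one site, and protocol 8.6.2 makes the ICON Medical Monitor its main contact for eligibility questions. That stands and limits the consequence, but it does not supply the missing limit.

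A reader might infer that nobody could be enrolled, or that every enrolled subject is a real eligibility violation. The documents do not support that. A cap inside the Grade 3 range is most likely a drafting slip, and protocol 2.2 shows that Day 60 interim data were in hand when the 100 mg dose was decided, so subjects had been dosed.

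A reader might also infer that the wording changes which measurement is the baseline. It does not: SAP 7.1 takes the latest measurement before dosing, and protocol 10.3.3.2 uses the admission value for laboratory data.

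**Conclusion.** The point holds in two parts. First, the upper limit in criterion 8 is unusable on the text as supplied: for every test it lies below the LLN that the same criterion requires, by a factor of between 2.4 (neutrophils, 1,700/700) and 7.5 (female hemoglobin, 10.9/1.46). This rests on the expression having been read correctly from the PDF. Second, criterion 8 and the Grade 1 rule give opposite answers for every general Grade 1 low value of hemoglobin, platelets, WBC and neutrophils, and for WBC the Grade 1 rule adds a competing upper limit. This part needs no assumption about the expression.

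The practical consequence is an undefined upper limit and a contradictory lower rule, which affect who is eligible and which deviations are recorded. How many subjects would be classified differently cannot be calculated, because the documents give no distribution of screening counts. The 11,000 figure for WBC is an assumption about intent.

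**What to change.** Check the expression in criterion 8 against the source document. Then correct the criterion so that it gives one explicit, usable upper limit for each of the four tests. State in protocol 6.5.2 and SAP 3.16 whether the Grade 1 rule applies to screening eligibility, and make criterion 8, those two sections and Appendix B agree, including the race-specific rows. The clinical team chooses the limits. For subjects already enrolled, record which reading was applied, so that the eligibility listing and the deviation summary can be interpreted.

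The cost is a one-line protocol correction with matching edits in 6.5.2 and SAP 3.16, plus the ethics approval that protocol 13.2 requires for an amendment. Sample size, endpoints and planned analyses do not change.

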4.1.2 Subject Exclusion Criteria

Subjects meeting any of the following exclusion criteria are not eligible for participation.

All must be answered no for the subject to be eligible for study participation

1. History of a chronic medical condition that would either interfere with the accurate assessment of the objectives of the study or increase the risk profile of the subject.
 - *Note: Chronic medical conditions include but not limited to diabetes; Asthma requiring use of medication in the year before screening; Autoimmune disorder such as lupus, Wegener's, rheumatoid arthritis, thyroid disease; Coronary artery disease; Chronic hypertension; History of malignancy except low-grade (squamous and basal cell) skin cancer thought to be cured; chronic renal, hepatic, pulmonary, or endocrine disease (except previous asthma which has required no treatment for the past year);*
2. History of severe allergic reaction of any type to medications, bee stings, food, or environmental factors or hypersensitivity or reaction to immunoglobulins.
 - *Note: Severe allergic reaction is defined as any of the following: anaphylaxis, urticaria, or angioedema*
3. A marked baseline prolongation of QT/QTc interval (e.g., repeated demonstration of a QTc interval >450 milliseconds)
4. Clinically significant abnormal electrocardiogram at screening.

- *Note: Clinically significant abnormal ECG results include but not limited to: complete left or right bundle branch block; other ventricular conduction block; 2nd degree or 3rd degree atrioventricular (AV) block; sustained ventricular arrhythmia; sustained atrial arrhythmia; two Premature Ventricular Contractions in a row; pattern of ST elevation felt consistent with cardiac ischemia; or any condition deemed clinically significant by a study investigator*

5. Positive serology results for HIV, HBsAg, or HCV antibodies
6. Febrile illness with temperature $\geq 38^{\circ}\text{C}$ within 7 days of dosing
7. Pregnant or breastfeeding
8. Donated blood within 56 days of enrollment
9. Known allergic reactions to any of the study product components present in the formulation or in the processing, as listed in the Investigator Brochure
10. Treatment with another investigational drug within 28 days of dosing
11. Treatment with a monoclonal antibody within 3 months of enrollment.
12. Receipt of antibody (e.g. TIG, VZIG, IVIG, IM gamma globulin) or blood transfusion within 6 months or within 5 half-lives of the specific product given
13. Active drug or alcohol use or dependence that, in the opinion of the investigator, would interfere with adherence to study requirements
14. Use of H1 antihistamines or beta-blockers within 5 days of dosing
15. Use of any prohibited medication within 28 days prior to study entry or planned use during the study period
 - *Note: Prohibited medications include immunosuppressives (except Nonsteroidal Anti-Inflammatory Drugs [NSAIDS]); immune modulators; oral corticosteroids (topical/intranasal steroids are acceptable); anti-neoplastic agents; any vaccine (licensed or investigational). Subjects will be eligible to receive any authorized COVID-19 vaccine after they complete Study Day 8*
16. Previous exposure to botulinum toxin, receipt of antibodies against botulinum toxin, or previous treatment with equine antitoxin
17. Any previous injection or planned injection within 4 months after enrollment of botulinum toxin for cosmetic reasons, spastic dysphonia, torticollis, or any other reason

18. Any specific condition that in the judgment of the investigator precludes participation because it could affect subject safety

19. Plans to enroll or is already enrolled in another clinical trial* that could interfere with safety assessment of the investigational product at any time during the study period
 - *Note: Includes trials that have a study intervention such as a drug, biologic, or device*

20. Is a study site employee or staff
 - *Note: Site employees or staff include the PIs and sub-investigators or staff who are supervised by the PI or Sub-Investigators*

21. Systolic blood pressure >140mm Hg or diastolic blood pressure >90 mm Hg
 - a. *Grade 1 values may be repeated once if the PI believes a transient condition led to the aberrant value and are allowable unless deemed clinically significant by the PI.*

22. Resting heart rate <50 or >100 beats per minute

23. Oral temperature $\geq 38^{\circ}\text{C}$ (100.4°F)

24. Subjects with NX02 antibody levels present at screening will be excluded from Cohort 4.

4.2 Treatment Assignment Procedures

4.2.1 Randomization Procedures

Randomized treatment assignments will be generated by a statistician at ICON PLC. Randomization will occur following admittance to the unit and confirmation of eligibility is confirmed.

This is a Phase 1 double-blinded, placebo-controlled trial that will randomize subjects within four dosing Cohorts to either active or placebo in an overall 4:1 ratio. For each dosing cohort, the first two subjects will be randomized in a 1:1 fashion to active and placebo to ensure that one of the first two subjects receives active treatment and the other control. An alternate subject will be admitted to the unit for each two-subject group. If one of the first two subjects is not randomized for any reason, then the alternate subject will receive the next consecutive randomization number. The product assignment of the remaining eight subjects in each cohort will be a simple random sample to ensure the 4:1 ratio for the dosing cohort. The randomization list will be generated by the unblinded study biostatistician and transferred to the unblinded study pharmacist prior to start of the study.

If 2 or more subjects withdraw, are lost to follow up or terminate prior to Day 8, those subjects need to be replaced to ensure that data for at least 7 subjects is available for review.

If 2 or more subjects withdraw, are lost to follow up or terminate prior to Day 60 or are not compliant with all PK draws through Day 15, they may be replaced.

If more than 2 subjects withdraw, are lost to follow up or terminate following the Day 8 SRC review of safety data, the site will attempt to replace those subjects in that dose group at the time of the next planned cohort.

